7.6 STUDY TERMINATION

The Sponsor reserves the right to temporarily halt and/or terminate the study (or if appropriate, individual treatment dose groups) at any time for safety, scientific or ethical reasons including, but not limited to:

- Emerging safety concerns from this study, other ongoing studies with ferric maltol, or new and relevant scientific information, which result in the risk-benefit ratio for this study becoming unfavorable, in the Sponsor's opinion.
- If the total number of dropouts is so high or the number of included subjects is so low that completion of the trial will not realistically be expected within a reasonable timeframe.
- If the Sponsor determines the study will no longer reveal new knowledge and consequently is ethically no longer justifiable.

In case of an early termination of the study or temporary halt by the Sponsor, the IEC and CA will be notified within 15 calendar days, including a detailed written explanation of the reasons for the termination/halt.

In all circumstances connected with temporary halt and/or termination of the study, the following principles will apply:

- All affected parties (such as the IEC, CA, Investigators, heads of study centers /clinic directors) must be informed as applicable according to local law.
- All study materials and supplies (except documentation that should remain stored at site) must be returned to the Sponsor/designee.

CONFIDENTIAL Page 48 of 80

8 TREATMENT OF SUBJECTS

Ferric maltol oral suspension will be supplied to study sites on behalf of Shield TX (UK) Ltd by Quay Pharma, [name]. The drug substance and drug product are manufactured, tested and controlled in accordance with Good Manufacturing Practice (GMP). Full details are documented in the Investigational Medicinal Product Dossier (IMPD) and current Investigator's Brochure. Sites must arrange storage of Investigational Medicinal Product in a temperature monitored, secure location which is accessible to authorised individuals only.

Ferrous sulfate oral liquid 125 mg/ml (25 mg/ml elemental iron) or equivalent dose will be used for all children/adolescents randomised to this group.

8.1 INVESTIGATIONAL MEDICINAL PRODUCT (IMP) PRESENTATION

 150 ml amber glass bottle with graduated syringe and adaptor. Oral suspension containing 30 mg elemental iron, in the form of 231.5 mg ferric maltol, in 5 ml suspension

A full list of excipients can be found in the Investigator's Brochure.

8.2 COMPARATOR

• Ferrous sulfate 125 mg/ml (25 mg/ml elemental iron) oral liquid or equivalent dose will be administered under this protocol.

8.3 PACKAGING

Oral suspension: Ferric maltol oral suspension will be supplied in an amber glass bottle with graduated syringes and adaptor.

8.4 STORAGE

IMP must be stored below 25 °C and must not be frozen. In the event that the drug is exposed to temperatures greater than or equal to 25°C, or to freezing, the CRA/Sponsor should be contacted for review and further instruction.

Ferrous sulfate oral liquid to be handled and stored according to SPC/PI.

8.5 LABELLING

All bottles will be identified by a unique Bottle ID number. Bottles will be clearly labelled as ferric maltol with the dose indicated. Labels of the IMP will contain information according to European Directives 2003/94/EC, 2001/20/EC and US 21 CFR 312.6.

CONFIDENTIAL Page 49 of 80

Individual supplies packaging and labelling will be checked by the Investigator/designee before the subject (aged 2-17 yrs) takes their first dose of study medication at site on Day 1 (Visit 2).

Packaging and labelling will be checked by the Investigator/Designee before the subject (aged 1 m - < 2 yrs) takes their single dose on the Pre-assignment PK visit.

8.6 TREATMENT ASSIGNMENT AND BLINDING

At randomisation, the Interactive Response Technology (IRT) will assign children aged 2 yrs to 17 yrs to either the ferric maltol or ferrous sulfate treatment group. The site will dispense the appropriate number of open-label ferric maltol bottles or ferrous sulfate at each scheduled study visit according to the schedule of assessments. Study Treatment and duration is specified in section 5.5.2 of this protocol.

Children aged 1 m - < 2 yrs: all subjects will receive ferric maltol oral suspension following satisfactory completion of the pre-assignment phase.

This is an open label study and treatment assignment is not blinded.

8.6.1 TREATMENT ASSIGNMENT

Subjects aged 2 yrs to 17 yrs will be randomised 1:1 to either treatment. Randomisation will be centrally controlled and stratified by age and gender as well.

The subject will be instructed to administer the first dose of ferric maltol oral suspension in the presence of the site staff on Visit 2 (infant age group Pre-assignment PK Day). Subsequent doses may need to be administered under the supervision of the child's parent or legal guardian and recorded on a dosing diary. The first 12 subjects in each age group (2 yrs - 9 yrs, 10 yrs - 17 yrs, respectively) will be instructed to withhold their morning dose of ferric maltol on PK Day 2 until pre-dose PK blood samples have been collected at the site.

If a subject forgets to take a dose, he/she should take the next dose as normal. The subject should not take a double dose to make up for a forgotten dose.

In the event of an administered dose not being consumed or partially consumed by the patient this will be noted as a missed dose and will not be repeated. Clear instructions will be provided by the Investigator to the parents/guardians who are supervising the drug administration and dosing diary.

Patient weight should be recorded at each clinic visit and drug dosing administered as per last clinic visit weight.

During the PK days:

- if the administered dose is not consumed or partially consumed by the patient this will be noted as a missed dose and will not be repeated. The PK sampling will be cancelled.
- -the site staff will record the timing of each meal, concomitant medication and its iron content within the eCRF.

8.7 TREATMENT COMPLIANCE

Subjects will be instructed to take the study drug as described in detail on the drug labels and by the Investigator/designee.

Subjects (ferric maltol and ferrous sulfate) will be instructed on Visit 2 to complete a dosing diary from the evening of Visit 2 until the next visit, in order to document the day and time that they took their morning and evening doses on those treatment days whilst at home. Subjects will be instructed to return all unused supplies medication packaging on their visits, having withheld their dose of ferric maltol on PK Day 2 morning. Compliance will be assessed from the dosing diary entries and reconciled using the drug accountability form.

If a subject is found to be non-compliant with the study medication (defined as less than 80% or more than 120% compliant with the dosage schedule), the subject/parent/legal guardian will be counselled and trained on the importance of maintaining adherence to study medication. If the subject is repeatedly non-adherent, a decision will be made by the medical monitor and/or Sponsor as to whether the subject should be withdrawn from the study treatment.

If the subject discontinues the study due to intolerance to either ferrous sulfate or ferric maltol, this should be documented in the eCRF.

Subjects who do not attend their visits may be withdrawn from the study. A copy of the relevant local SPC/PI for ferrous sulfate will be available in the Investigator Site File (ISF). Special safety information and warnings/precautions relating to the drug will be highlighted to the Investigator during the Site Initiation Visit (SIV).

The delivery of medication to the site, its use and return, as well as subject-specific compliance, will be reconciled and documented using a Drug Accountability Form in order to monitor compliance with the medication schedule. All opened containers, together with remaining contents, and unopened containers will be kept by the Investigator in a secure, locked area until return to the drug supplier by the monitor or destruction by the site if agreed with the Sponsor/designee. The Investigator will use the IMP only within the framework of this clinical study and in accordance with the current, approved study protocol.

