5.4.2 Phase I studies in adults

ST10-01-101 study

Another open-label, randomised Phase 1 study evaluated the pharmacokinetics of ferric maltol and its effect on iron indices in patients with iron deficiency (with or without anaemia). 24 subjects received ferric maltol 30, 60, or 90 mg BID over an 8-day period. PK and iron uptake were assessed on Days 1 and 8. Ferric maltol showed predictable pharmacokinetics, no accumulation over 7 days, and improvements in iron uptake across the dose range 30–90 mg BID (Bokemeyer, 2016).

The PK data from this study are consistent with previous data indicating that maltol is rapidly glucuronidated and renally excreted after ferric maltol dosing, while iron is independently absorbed. Across the three dosing regimens investigated, exposure to maltol glucuronide increased dose proportionally. Serum iron concentrations and TSAT values generally increased with higher doses, but there was no clear relationship between these parameters and exposure to maltol or maltol glucuronide. Higher NTBI levels were detected in the higher dosing regimens. Although the frequency of AEs was also higher with these dosing regimens, there is no evidence that this was a consequence of elevated NTBI in these subjects. The reported AEs were consistent with the established safety profile of ST10.

ST10-01-102 study

The pharmacokinetics (PK) and iron uptake of 30 mg ferric maltol BID were confirmed in a cohort of 15 IBD patients participating in the open-label phase of studies ST10-01-301 and ST10-01-302 (Shield TX, data on file for sub-study ST10-01-102). Plasma concentrations of

CONFIDENTIAL Page 26 of 80

maltol above the limit of assay detection were transiently observed between 15 min and 4 h after dosing (mean C_{max} 67.3 ng/mL; median T_{max} 1.0 h; mean AUC 136 h*ng/mL; mean t 1/2 term 0.8 h). However, consistent with earlier studies of ferric maltol, maltol glucuronide predominated in plasma (mean C_{max} 4677 ng/mL; median T_{max} 1.0 h; mean AUC 9651h*ng/mL and mean t ½ term 1.1 h). Maximal change in serum iron and TSAT was observed 2 h after dosing, however in many subjects it was apparent from the TSAT rises that iron uptake was occurring from 30 minutes. The inter-subject variability for AUC of both maltol and maltol-glucuronide in this cohort was low (approximately 27%).

ST10-01-104 study

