An open-label, Phase I, randomised, 4-way crossover study was completed to evaluate the PK and iron absorption after a single 30 mg dose of ferric maltol administered as a capsule or oral suspension (fasted and fed condition) via primary parameters C_{max} and AUC_{last}.

Both capsule and suspension of ferric maltol in fasted and fed conditions were readily absorbed with mean serum iron concentrations returning to baseline or slightly below at 24 hours.

For the fasted condition, comparing the suspension versus the capsule, the ratios of C_{max} , AUC_{last} , and AUC_{inf} geometric LS means (90% Confidence Interval (CI)) for serum iron findings indicated that, in the fasted condition, ferric maltol capsule and suspension had different PK with respect to C_{max} but a definitive difference in PK was not observed with respect to AUC_{last} and AUC_{inf} .

For the suspension formulation comparing fasted versus fed conditions, the ratios of C_{max} , AUC_{last} , and AUC_{inf} geometric LS means (90% CI) findings indicate that the ferric maltol suspension had similar PK when administered in fasted or fed conditions with respect to C_{max} and AUC_{last} .

For the fed condition, comparing the suspension versus capsule the ratios of C_{max} , AUC_{last} , and AUC_{inf} geometric LS means (90% CI) for serum iron indicate that, in the fed condition, ferric maltol capsule and suspension had similar PK with respect to C_{max} and AUC_{last} and a definitive difference in PK was not observed for AUC_{inf} .

The baseline corrected serum iron and TSAT, were consistent with the primary endpoint findings, although the formulation effect and capsule food effect differences were more marked with baseline corrected serum iron.

It is noted that the overall exposure of maltol and maltol glucuronide are less influenced by physiological iron status compared to the iron PK parameters.

There were no apparent differences between the formulations (suspension versus capsule) in the number of AEs and no study drug-related TEAEs were reported for either formulation.

CONFIDENTIAL Page 27 of 80

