6 STUDY OBJECTIVES AND ENDPOINTS

6.1 PRIMARY OBJECTIVES:

- To compare the safety and gastrointestinal tolerability of ferric maltol oral suspension and ferrous sulfate oral liquid in children and adolescents aged 2 years to 17 years and assess the safety and tolerability of ferric maltol oral suspension in children 1 month to less than 2 years, in the treatment of iron deficiency anaemia during the 12 weeks treatment period.
- 2. To assess the effect on haemoglobin in children and adolescents aged 1 month to 17 years after twice daily ferric maltol oral suspension administration for 12 weeks

6.2 SECONDARY OBJECTIVES:

- 1. To assess the pharmacokinetics (PK) in children and adolescents aged 2 to 17 years after a single dose of ferric maltol oral suspension on Visit 2 (PK Day 1), and after twice daily administration for at least 6 days, on Visit 3 (PK Day 2), after a single morning dose, through measurement of serum iron, corrected serum iron, transferrin saturation (TSAT) and plasma maltol and maltol glucuronide
- 2. To assess the effect on iron markers in children and adolescents aged 1 month to 17 years after twice daily ferric maltol oral suspension administration for 12 weeks
- 3. To assess the PK, in children aged 1 month to less than 2 years of age after a single dose of ferric maltol oral suspension (Pre-assignment PK visit) and after twice daily administration for at least 6 days, on Visit 3 (PK Day 2), after a single morning dose, through measurement of serum iron, corrected serum iron, transferrin saturation (TSAT) (PK Day 2 only), plasma (PK Day 2 only) and urine concentration of maltol and maltol glucuronide
- 4. To assess the effect, in children aged 1 month to less than 2 years of age after twice daily administration for at least 6 days, on Visit 3 (PK Day 2) after a single morning dose, on serum transferrin, total and unsaturated iron binding capacity (TIBC, UIBC)
- 5. To assess the effect, in children aged 2 to 17 after a single dose of ferric maltol suspension Visit 2 (PK Day 1), and after twice daily administration for at least 6 days, on Visit 3 (PK Day 2) after a single morning dose, on serum transferrin, total and unsaturated iron binding capacity (TIBC, UIBC).
- 6. To compare the palatability from age-appropriate scoring system of ferric maltol oral suspension and ferrous sulfate oral liquid

CONFIDENTIAL Page 40 of 80

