10.3 SCHEDULE OF ASSESSMENTS FOR SUBJECTS AGED 2 YEARS-17 YEARS

	SCREENING	TREATMENT					FOLLOW-UP
Duration	Up to 21 days	12 WEEKS (equivalent of 84 days)					10-14 days
Day		1	7-10	28	56	84	94-98
Visit ¹¹	1	2	3 ³	4	5	6	7 ^{9,10}
Informed Consent	х						
Eligibility ^{1,8}	х	х					
Demographics	х						
Medical History	х						
Physical Examination	х					х	
Vital Signs ²	х	х	Х	X	х	х	
Urine Pregnancy Test ⁴	х	х	х	х	х	х	
Clinical Laboratory tests ⁵	х					х	
Haematology ⁶	х			X		х	
Iron markers ⁶	х			Х		Х	
PK assessment PK Blood Sampling for maltol/maltol glucuronide and iron markers ⁷		х	х				
Randomisation ⁸		х					
Dispense Study Drug		х	х	х	х		
Return Study Drug for Accountability			х	х	х	х	
Palatability questionnaire		х		х			
Adverse Events		х	х	х	х	х	х
Concomitant Medications and Procedures	х	х	х	х	х	x	х
Compliance reminder		х	х	Х	х	х	
Compliance assessment			х	Х	х	Х	

CONFIDENTIAL Page 56 of 80

- 1. A subject may be retested once for laboratory criteria that do not meet protocol criteria so long as randomisation occurs no more than 21 days from the initial screening visit date (if eligible).
- 2. Vital Signs body weight, height, systolic/diastolic blood pressure, pulse, and body temperature at each visit. Patient weight should be recorded at each clinic visit and drug dosing administered as per last clinic visit weight.
- 3. Visit 3 (PK Day 2) only applicable for the first 12 subjects randomised to ferric maltol group in each age group (2 yrs -9 yrs, 10 yrs-17 yrs).
- 4. Urine pregnancy test for female subjects of childbearing potential only.
- 5. Clinical Laboratory tests including:
 - a. Clinical Chemistry: Vitamin B12, folate, ALT, AST, alkaline phosphatase, gamma-glutamyl transpeptidase (GGT), total bilirubin, creatinine, amylase, blood urea nitrogen (BUN), phosphorous, sodium, potassium, chloride, calcium, total cholesterol, uric acid, glucose, total protein, albumin
- 6. Haematology and Iron markers:
 - a. Haematology: Red blood cell count, haemaglobin, haematocrit, mean cell volume (MCV), white blood cell count (total and differential (% and absolute), absolute reticulocyte count and platelet count.
 - b. Iron Markers: serum iron, transferrin, transferrin saturation (TSAT), total and unsaturated iron binding capacity (TIBC, UIBC) and ferritin.

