3.1.3 Definition of Baseline

Baseline is defined as the last measurement prior to the first treatment dose of study drug.

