3.1.5 Hypothesis Testing

Hypothesis testing will be performed for the interim analysis to test the hypothesis that the ferric maltol Hb change from baseline to Week 12 is > 0. If an interim analysis is conducted, a Pocock spending function will be used; the interim analysis will be based on a (100-3.45)% two sided confidence interval.

The efficacy primary endpoint will also involve hypothesis testing. If no interim analysis is conducted the hypothesis testing will be based on a 95% two-sided confidence interval. If the study does not stop after the interim analysis, the final analysis will be based on a (100-2.57)% two sided confidence interval.

The study safety primary endpoints will be analysed by descriptive statistics only. The secondary endpoints will be analysed by descriptive statistics only. Thus, no formal testing strategy or adjustments of the Type I error will be employed for the evaluation of secondary endpoints.

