3.4.2 Secondary Endpoints Analysis

The secondary endpoints will be reported for each treatment group using descriptive statistics summarised by mean, median, and range (minimum and maximum), and 95% confidence interval for the mean where applicable, split by age group.

Any measurement obtained after a patient received a blood transfusion, or received an intravenous iron or erythropoiesis stimulating agent (ESA) will be excluded from the analysis.

The secondary endpoints are as follows: PK analysis of Serum Iron, Corrected serum iron, TSAT, Transferrin, TIBC, UIBC, Maltol and Maltol Glucuronide.

Descriptive summary statistics will be summarised for children and adolescents aged 1 month to 17 years in the ferric maltol group for the PK analysis of Serum Iron, Corrected serum iron, TSAT, Transferrin, TIBC, UIBC, Maltol and Maltol Glucuronide.

Changes in iron markers from baseline to Weeks 4 and 12

The secondary analysis of the change from baseline to Weeks 4 and 12 in iron markers (serum iron, serum corrected iron, transferrin, TSAT, TIBC, UIBC and ferritin) will be summarised using descriptive summary statistics. In this analysis, missing Week 12 and Week 4 values will be imputed using a LOCF (last observation carried forward) approach in which the last available post-baseline measurement will be used in the analysis.

Achieving Hb concentration within normal range at Week 12

The number and percentage of subjects achieving normal range, based on the central laboratory's normal reference range, at Week 12 will be summarised by treatment group.

Qualitative assessments from subject questionnaires that allow evaluation of the acceptability, palatability and ease of use

Qualitative assessments from subject questionnaires that evaluate acceptability, palatability and ease of use will be summarised separately for children aged 5 and under and those aged 6 and over.

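### Week 4 and Week 12 iron markers are drawn at no stated time relative to the study dose, so changes in serum iron, TSAT and UIBC can include an acute post-dose component.

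*Protocol*

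**What the plan says.** Secondary objective 2 (Protocol 6.2) reads "To assess the effect on iron markers in children and adolescents aged 1 month to 17 years after twice daily ferric maltol oral suspension administration"; the treatment period is 12 weeks. The panel in Protocol 10.3 is "Iron Markers: serum iron, transferrin, transferrin saturation (TSAT), total and unsaturated iron binding capacity (TIBC, UIBC) and ferritin". Ages 2 to 17 have it at screening, Visit 4 (Day 28) and Visit 6 (Day 84). Under Protocol 10.4, infants have it at screening, at Visit 2 before assignment, and at Visit 6. They have no iron markers at Visit 4. The footnotes list the analytes but give no time relative to dosing at Visits 4 and 6.

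Study drug is taken morning and evening (Synopsis). Holding the morning dose until blood is drawn is required only on PK Day 2 (Protocol 7.1 and 8.6.1); Protocol 8.7 repeats it as "having withheld their dose of ferric maltol on PK Day 2 morning".

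SAP 3.1.3 says "Baseline is defined as the last measurement prior to the first treatment dose of study drug". SAP 3.4.2 covers "The secondary analysis of the change from baseline to Weeks 4 and 12 in iron markers" with descriptive statistics and LOCF. It excludes values after transfusion, intravenous iron or an ESA, and has no rule on time since dose. SAP 3.1.5 adds "The secondary endpoints will be analysed by descriptive statistics only".

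On the acute response, Protocol 5.4.2 reports "Maximal change in serum iron and TSAT was observed 2 h after dosing" in one adult study. In another, capsule and suspension "were readily absorbed with mean serum iron concentrations returning to baseline or slightly below at 24 hours".

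**The concern.** A change from baseline in iron markers is meant to show the effect of 12 weeks of treatment on iron status. Serum iron and TSAT also move within hours of a single dose. A child who takes the morning dose at home and attends mid-morning may be bled near the peak. Another who attends before dosing is bled about 12 h after the evening dose. The plan averages both and compares them with a baseline at which no study-drug treatment was under way.

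Serum iron and TSAT are then pushed up, and UIBC down, by an amount that depends on clinic logistics. What is at stake is how these three secondary summaries are read. No test, error rate or power figure changes.

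**Working it through.** The plan states no power, error rate or expected change for this endpoint, so there is no figure to reproduce. The check has four steps.

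**1. Timing rules side by side.**

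| Sample | Time relative to dose |
|---|---|
| Baseline | Before first treatment dose (SAP 3.1.3) |
| PK Day 2 | Pre-dose, then fixed post-dose windows (Protocol 10.3, 10.4) |
| Visit 4, ages 2 to 17 | None stated |
| Visit 6, all ages | None stated |

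The analytes whose timing is controlled on PK days are uncontrolled at the visits that supply the Week 4 and Week 12 endpoint.

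**2. How much of a peak could remain at the draw.** The documents give the time of peak (2 h) and show means at or below baseline at 24 h, but not the curve between. Assume a single-dose triangle with peak height 1: f(t) = t/2 up to 2 h, then (E − t)/(E − 2) down to zero at E hours. Average f over evenly spread draw times. For E = 12 and draws from 0.5 to 6 h: [(2² − 0.5²)/4 + (10² − 6²)/(2 × 10)] / 5.5 = (0.94 + 3.20)/5.5 = 0.75.

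| Assumed return to baseline, E | Draws 0.5 to 6 h after dose | Draws 10 to 14 h after dose (pre-dose under twice-daily dosing) |
|---|---|---|
| 6 h | 53% | 0% |
| 12 h | 75% | 5% |
| 24 h | 83% | 55% |

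**3. What that could do to the endpoint.** No absolute rise is given, so assume a peak of 25 to 100 µg/dL, a mean share present of 25% to 75%, and TIBC fixed at 400 to 450 µg/dL.

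- Serum iron shift = share × peak: 0.25 × 25 = 6.25, up to 0.75 × 100 = 75 µg/dL.
- UIBC shift: since TIBC = serum iron + UIBC, the same amount downward.
- TSAT shift = 100 × iron shift / TIBC: 100 × 6.25/450 = 1.4, up to 100 × 75/400 = 18.8 percentage points.

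All of this would occur with iron stores unchanged. The ranges are illustrations, not estimates for this trial.

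**4. Whether the arms are affected equally.** For an assumed 30 kg child aged 2 to 11, Protocol 5.5.2 gives 15 mg per ferric maltol dose and 3 × 30 = 90 mg per ferrous sulfate dose, a ratio of 6 in ingested iron. Protocol 5.5 puts ferric maltol availability at 24% and says iron salts can be below 10%. Available iron is then 15 × 0.24 = 3.6 mg against at most 90 × 0.10 = 9 mg at that limit, a ratio of 2.5 or less. Protocol 5.4.3 also found paediatric Day 10 iron exposure comparable across 7.8, 16.6 and 30 mg of ferric maltol. These figures do not establish equal acute rises in the two arms, and they do not measure the difference.

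**The case against.** **Timing may be set elsewhere.** Protocol 10.8.1 sends collection procedures to a Laboratory Manual, and Section 9 sends procedural detail to the Investigator Site File. Neither is available here, so a timing rule may exist. If so, nothing in the protocol or SAP points to it, and the analysis text does not rely on it.

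**Visit 4 practice may help.** Protocol 10.8.4 lets the palatability dose be taken on site, or at home after the visit. That makes an earlier dose that day less likely, but it does not fix the order of dose and blood draw, and it does not apply at Visit 6.

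**The PK evidence is indirect.** The 2 h figure comes from 15 adults with IBD in the capsule studies. This trial gives suspension after meals. Protocol 5.5 reports fasted suspension Cmax at 69.94% of capsule, and capsule Cmax 47% higher fasted than fed. The rise here may be smaller than those data suggest. This limits its size but does not show it to be absent.

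**The endpoint is limited in role.** It is secondary and descriptive, and objective 2 concerns ferric maltol only. The argument does not extend to ferritin, transferrin, TIBC or haemoglobin, so repletion can still be judged from those. This stands, and it sets the weight of the point.

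**Stronger readings that the documents do not support.** A reader might infer that serum iron stays raised until 24 h; the study reports where means stood at 24 h, not how long they were raised. A reader might take the six-fold ratio of ingested iron as the ratio of bias between arms; step 4 shows that it is a poor proxy. A reader might also take baseline as iron-free. It is only off study drug: stable over-the-counter iron is allowed (Protocol 7.4.2), and infants have already had one pre-assignment dose.

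**Conclusion.** The point holds for Week 12 at all ages and for Week 4 at ages 2 to 17. As written, the plan lets an acute post-dose component, varying from child to child, enter the change in serum iron and TSAT (upward) and UIBC (downward). The direction rests on the protocol's adult PK data and on the identity linking TIBC, serum iron and UIBC.

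The size cannot be computed, because both the rise and the share of children sampled soon after a dose are unknown. Under the assumed ranges it runs from minor (about 6 µg/dL, 1.4 TSAT points) to large (75 µg/dL, about 19 points). Equal size in the two arms cannot be assumed. Haemoglobin and all formal testing are unaffected.

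A reader might infer that a pre-dose sample would be clean. Under twice-daily dosing it falls about 12 h after the evening dose, and in the assumed curves 0% to 55% of the peak remains. A pre-dose draw reduces the component and makes it more uniform, but may not remove it.

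LOCF adds a related gap. SAP 3.4.2 carries forward the last post-baseline value without barring post-dose PK-day samples, so a PK subject who leaves early could have a near-peak value carried to Weeks 4 and 12.

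**What to change.** 1. In Protocol 10.3 (Visits 4 and 6) and 10.4 (Visit 6 only), state that the iron-marker blood sample is collected before that morning's study dose is given. This is the sampling order already used on PK Day 2; dose amount, regimen and number of samples do not change. If the Laboratory Manual already sets a time, cite it and align the documents.
2. Record the date and time of the last dose and of the blood draw at these visits. Protocol 8.7 specifies diary dose times from the evening of Visit 2 only up to the next visit, so times before Visit 6 should not be taken for granted.
3. In SAP 3.4.2, keep the all-samples summary. Add a supportive summary of change in serum iron, TSAT and UIBC by time since last dose (pre-dose versus after that morning's dose) where both times exist. For children already sampled this is a sensitivity display, not a replacement: who had dosed is not random, and restricting to the undosed would select on behaviour after randomisation.
4. Exclude post-dose PK-day samples as a source for LOCF.

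The cost is a small change to visit instructions, two recorded times and one derived variable. Some children will lack usable times for the supportive summary.
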